# 4. OJECTIVE AND ENDPOINTS

	Objective	Endpoint [at 28 days]	Variable			
Primary	•To assess the safety and tolerability of escalating doses of topically applied Bisphosphocin Nu-3 Gel	Treatment emergent events related to clinical investigational product	
 
Vital signs
 
Safety laboratory analysis
 
Local wound/skin assessments
 
Physical examination
 
Adverse events
 
			
Secondary	
 
To assess the clinical effects of Nu-3 on cDFU
 
To assess antimicrobial effects of Nu-3 on wound microflora.
 
To support determination of the appropriate dose range of Nu-3 to be employed in future clinical studies.
 
	
 
Advanced digital imaging wound assessment post debridement
 
Pre and Post debridement digital pictures taken by clinical staff.
 
Changes in wound microbial population pre debridement
 
Recommended Phase 2 Dose (RP2D)
 
	
 
Ulcer surface area
 
Ulcer depth
 
Culture and microflora microbiological analysis
 
			

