# 6. STUDY POPULATION

#### **Inclusion criteria**

- 1. Men and women at least 18 years of age and up to 80 years of age, inclusive.
- 2. Voluntary written consent, given before performance of any clinical investigation-related procedure, and with the understanding that consent may be withdrawn at any time without prejudice to future medical care
- 3. Non-hospitalized ambulatory subjects suffering from diabetes mellitus, Type I or II per ADA criteria
- 4. The target ulcer is classified as grade 1 ulcer according to a Wagner Scale. These ulcers are superficial, full-thickness ulcers limited to the dermis, not extending to the subcutis.
- 5. Target ulcer is between 2 and 10 cm2 post debridement at screening and baseline.
- 6. The target ulcer must be no higher than the ankle (on or below the malleolus (ankle bone) with  $\geq 50\%$  below the malleolus.
- 7. Presence of a persistent cDFU for at least 4 weeks and not more than 1 year that has failed to respond to standard of care
- 8. Adequate vascular perfusion as evidenced by one of the following
  - a. Dorsal transcutaneous oxygen measurement (TCOM) or a skin perfusion pressure (SPP) measurement of ≥ 40 mmHg
  - b. Ankle Branchial Index (ABI) between 0.7 and 1.3 within 3 months of Screening using the extremity with the target ulcer
  - c. Arterial Doppler ultrasound evaluating for biphasic or triphasic dorsalis pedis and posterior tibial vessels at the level of the ankle or a TBI (Toe Brachial Index) of > 0.6 is acceptable
- 9. Subject has a caregiver who is able to attend baseline visit and apply wound treatment and study dressings for the study duration
- 10. Subject completed protocol-defined standardized wound care during the Screening and Run-in periods leading up to Day 0.
- 11. Must meet one of the following criteria:
  - a. Female subjects of Non-Child-Bearing Potential defined as:
    - i. Postmenopausal for at least 1 year, or surgically sterilized (i.e., hysterectomy or bilateral oophorectomy more than 3 months prior to Screening), or
    - ii. Bilateral tubal ligation more than 6 months prior to Screening
    - iii. Must have a negative serum  $\beta$ -hCG pregnancy test at screening and not be breastfeeding prior to being administered with the study drug.
  - b. Male subjects of Non-Childbearing Potential defined as those vasectomized subjects whose vasectomy was performed 6 months prior to Screening or those diagnosed as sterile by a physician.

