- Run-in Ulcer Assessment: Visual examination of chronic ulcer before and after debridement
- Sharp excisional debridement is allowed if necessary at Investigator's discretion
- Pre and post debridement digital photos taken by site personnel, if debridement is required. Two
  photos are to be taken from a focal distance of 18 inches, and one photo taken close-up for a total
  of three digital images
- Employ an advanced digital imaging system to accurately measure the target foot ulcer dimensions following debridement
- Evaluate wound healing and discontinue any subject with a  $\ge 30\%$  or greater reduction in area as shown by the advanced digital imaging measurements
- Continued offloading applied in accordance with Appendix 6
- Hydrogel and SOC dressing applied in accordance with the Appendix 4

Visit 3 (Day 0) Baseline: All subjects will return after the screening period for assessment of study participation criteria and if these are satisfied, the subjects will be randomly assigned to Nu-3 gel or placebo gel treatment. Subject disease assessments will be performed as specified in the schedule of events table.

- Vital signs measurements: Weight, temperature, resting blood pressure, heart rate, and respiratory rate. Vital signs are to be obtained prior to collecting laboratory samples
- Urine pregnancy test for WOCBP prior to randomization.
- Serum pregnancy test will also be conducted for WOCBP

- 12 Lead ECG
- Safety Laboratory tests
- Baseline Ulcer Assessment: Visual examination of chronic ulcer before and after debridement (if required, only LIGHT debridement is allowed)
- Two wound swabs, one for culture and one for microflora examination are taken BEFORE debridement
- Light debridement, only if required
- Digital photos should be taken pre and post debridement, if debridement is required. Two photos
  are to be taken from a focal distance of 18 inches, and one photo taken close-up for a total of three
  digital images
- Employ an advanced digital imaging system to accurately measure the target foot ulcer dimensions following debridement
- Subject randomized within electronic RTSM, obtaining kit number
- Subjects will be provided with his/her first designated test product kit and instructed to apply the product twice daily for 1 weeks (7±2 days). Test product application will be demonstrated, and subject instruction sheet reviewed, using the assigned test product

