- Take digital images with sponsor provided camera both pre and post debridement, if debridement is required. Two photos are to be taken from a focal distance of 18 inches, and one photo taken

- close-up for a total of three digital images
- Employ an advanced digital imaging system to accurately measure the target foot ulcer dimensions following debridement (if debridement is performed, only light debridement may be performed).
- Two wound swabs, one for culture and one for microflora examination are taken BEFORE debridement, if the wound is still open
- Collect kit dispensed on Day 14, determine accountability
- Subjects will be provided with his/her fourth and final designated test product kit and instructed to apply the product twice daily for 1 week (7±2 days).
- The subject will be scheduled for the next study visit, with a reminder to bring the test article kit and all tubes including empty, partially used and unused tubes to the visit.
- Record all adverse events (local and systemic), concurrent procedures, and changes in concomitant medications during the study on the source documents and case report forms (eCRFs).
- Continue offloading applied in accordance with Appendix 6

Visit 7 (Day 28±2 days): The study subject will return for final efficacy evaluation to the clinical site on Day 28±2 days. At that visit, the subject will undergo the following procedures and evaluations.

- Vital signs measurements: Weight, temperature, resting blood pressure, heart rate, and respiratory rate. Vital signs are to be obtained prior to collecting laboratory samples
- 12 Lead ECG
- Safety Laboratory Tests
- Serum pregnancy
- Ulcer Assessment: Visual examination of chronic ulcer.
- No debridement to be performed at this visit
- Two wound swabs will be taken, one for microbiological culture and one for microflora examination (unless ulcer has completely re-epithelialized).
- Take digital photos with the digital camera provided by sponsor. Two photos are to be taken from a focal distance of 18 inches, and one photo taken close-up for a total of three digital images
- Employ an advanced digital imaging system to accurately measure the target foot ulcer dimensions.
- Collect kit dispensed on Day 21, perform drug accountability
- Record all adverse events (local and systemic), concurrent procedures, and changes in concomitant medications during the study on the source documents and case report forms (eCRFs).

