- Continue offloading applied in accordance with Appendix 6

If the ulcer remains open at visit 7, subjects will be given a supply of non-abrasive bandages and written instructions on weekly ulcer care until the Day 42 follow up visit (Visit 8). In addition, subjects will be told to call if there is any worsening of the ulcer with regard to pain, signs of infection, or swelling.

Standardized offloading will continue until the final study visit (Day 42±2 days) regardless of wound healing status.

Visit 8 (Day 42±2) End of Study (EOS) Visit: The subject shall attend final end-of-study 42±2 days post

Randomization. At this follow-up visit, the subject will undergo the following procedures and evaluations.

- Vital signs measurements including weight, temperature, resting blood pressure, heart rate, and respiratory rate. Vital signs are to be obtained prior to collecting laboratory samples
- 12 Lead ECG
- Physical examination
- Safety Laboratory Tests
- For females of child-bearing potential: pregnancy test (serum) to be performed
- Ulcer Assessment: Visual examination of chronic ulcer.
- Take digital photos with the digital camera provided by sponsor. Two photos are to be taken from a focal distance of 18 inches, and one photo taken close-up for a total of three digital images
- Employ an advanced digital imaging system to accurately measure the target foot ulcer dimensions
- Record all adverse events (local and systemic), concurrent procedures, and changes in concomitant medications during the study on the source documents and case report forms (eCRFs)
- Physician may perform or not perform debridement according to his practice standards
- Offloading ends

Early Termination Visit: If a subject withdraws prior to completing the study, the reason for withdrawal will be documented. If a subject withdraws early due to a Serious Adverse Event, he/she will be followed until resolution/stabilization of the SAE.

If a subject prematurely withdraws from the study, subject will be asked to complete the study procedures and evaluations performed in the final study visit at the time of withdrawal from the study:

- Vital signs measurements including weight, temperature, resting blood pressure, heart rate, and respiratory rate. Vital signs are to be obtained prior to collecting laboratory samples
- 12 Lead ECG
- Physical examination
- Safety Laboratory Tests
- For females of child-bearing potential: serum pregnancy test to be performed.

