# **Definitions**

## Baseline

For all parameters, baseline will be defined as the last available data point just prior to the first treatment, which occurs at visit 3.

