#### Percentage area reduction from baseline

The percent change in the surface area of the Index Ulcer (PAR) will be calculated using the following formula:

((A1-A2)/A1)\*100

Where A1 is the baseline area (at randomization), and A2 is the area at the specified time point.

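### Percentage area reduction can mix debridement states: the baseline area follows light debridement in some subjects, the Day 28 area never does, and the Day 42 order is not settled

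*Protocol*

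**What the plan says.** - **Formula.** The SAP defines PAR as ((A1-A2)/A1)*100: "Where A1 is the baseline area (at randomization), and A2 is the area at the specified time point". For all parameters, "baseline will be defined as the last available data point just prior to the first treatment, which occurs at visit 3". Neither definition mentions debridement.
- **Visit 3 (Protocol Section 8).** The imaging instruction is "Employ an advanced digital imaging system to accurately measure the target foot ulcer dimensions following debridement". The debridement instruction is "Light debridement, only if required". Inclusion criterion 5 (Section 6) is in the same terms: "Target ulcer is between 2 and 10 cm2 post debridement at screening and baseline".
- **Visits 4 to 6.** Debridement is again light and conditional.
- **Visit 7.** "No debridement to be performed at this visit". Footnote 3 to the Schedule of Events confirms that all images are still captured. The objectives tables (Synopsis and Section 4) nevertheless list, under a 28-day column heading, "Advanced digital imaging wound assessment post debridement".
- **Visit 8.** The visit list gives imaging first and later adds "Physician may perform or not perform debridement according to his practice standards". Appendix 4 allows either sharp or light debridement there. The Schedule of Events marks Visit 8 in an imaging row headed as post-debridement, without the footnote that Visit 7 and early termination carry.
- **Reporting.** The SAP plans a weekly PAR plot and table by treatment group, names no last week, and imputes missing continuous outcomes by last observation carried forward (LOCF).

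**The concern.** PAR is interpretable as healing only if A1 and A2 are measured in the same state. Appendix 4 describes light debridement as including, where there is an edge effect, trimming the margin back to adherent epidermis, so debridement can move the measured border outward. A debrided baseline set against an undebrided Day 28 area then shows a reduction that is not healing. An area imaged after sharp debridement at Day 42 does the reverse. The weekly course could show steps at Days 28 and 42 that come from procedure alone, and LOCF can carry an area from one state into a visit measured in another. The result at stake is absolute PAR, part of the secondary ulcer-area evidence. The secondary objectives also include supporting the choice of dose range for later studies.

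**Working it through.** **No plan figure to reproduce.** The documents give no expected PAR, SD or power, no figure for enlargement by debridement, and no expected share of subjects debrided.

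**Inputs.** From the documents: the PAR formula and the visit rules above. Assumed: *e*, the proportional enlargement of the measured area by light debridement (5% to 30%); *s*, the same for sharp debridement (20% in the example); *q*, the share of subjects debrided at Visit 3. Let *t* be the PAR that would be seen if both areas were measured after light debridement.

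**Day 28, subject debrided at Visit 3.** A1 is enlarged by (1+e) and A2 is not. Observed PAR = 1-(1-t)/(1+e), so bias = (1-t)·e/(1+e). In percentage points:

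| e (assumed) | t = 0 | t = 30% | t = 50% | t = 80% |
|---|---|---|---|---|
| 5% | +4.8 | +3.3 | +2.4 | +1.0 |
| 10% | +9.1 | +6.4 | +4.5 | +1.8 |
| 20% | +16.7 | +11.7 | +8.3 | +3.3 |
| 30% | +23.1 | +16.2 | +11.5 | +4.6 |

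Example: a baseline of 4.00 cm² after debridement, with no real change and e = 10%, is imaged at Day 28 as 4.00/1.10 = 3.64 cm². PAR = 0.36/4.00, about 9%.

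**Day 28, subject not debrided at Visit 3.** Both areas are undebrided, so the bias is 0.

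**Group mean at no true change.** Bias = q·e/(1+e). For e = 5%, 10%, 20%, 30%:
- q = 0: 0 throughout.
- q = 50%: +2.4, +4.5, +8.3, +11.5 points.
- q = 100%: +4.8, +9.1, +16.7, +23.1 points.

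**Day 42, if imaged after sharp debridement.** For a subject debrided at Visit 3, observed PAR = 1-(1-t)(1+s)/(1+e). With e = 10% and s = 20%:
- t = 0: 1-1.20/1.10 = -9.1%. Day 28 read +9.1%, a step of -18.2 points with no real change.
- t = 50%: 1-0.50×1.20/1.10 = 45.5%. Day 28 read 54.5%, a step of -9.1 points.

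If Visit 8 is imaged before debridement, it matches Visit 7 and this step disappears.

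**Between arms.** With equal e, q and t in both arms, the biases cancel and the difference is 0. If, with t = 30% and all subjects debrided at Visit 3, e were 5% on active and 15% on placebo, the readings would be 33.3% and 39.1%, a difference of -5.8 points; reversing e gives +5.8. Chance alone can also unbalance q: at a 50% share, with 12 subjects on one active dose and 8 on placebo, the SD of the difference in share is √[0.25(1/12+1/8)] = 0.23. At e = 20% and no true change, that is 0.23×16.7, about 4 PAR points.

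**The case against.** The strongest defence has four parts.

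1. **Most of the mismatch may never arise.** Visit 3 debridement is light and conditional, and it follows required sharp debridement at Visit 1 and permitted sharp debridement at Visit 2, which may leave little to remove. This stands, and it is why the size must be scaled by the share debrided. A reader might infer that every baseline is post-debridement and that Day 28 PAR is therefore inflated throughout; the visit text does not support that.
2. **The enlargement is unquantified.** Appendix 4 makes the direction plausible, but edge trimming is itself conditional and healthy granulation tissue is to be protected. Nothing in the documents supports a particular figure. This also stands: the percentages illustrate sensitivity and are not estimates.
3. **The Visit 7 exception is disclosed.** Footnote 3 states it, and the Visit 7 imaging line drops the reference to debridement. Sites therefore know what to do at Visit 7. The endpoint label and the SAP formula are still left unreconciled with it.
4. **Day 42 is follow-up.** The endpoint column is for 28 days, Visit 7 is called the final efficacy evaluation, and the Visit 8 list puts imaging ahead of debridement. But list order is not an instruction, the schedule row points the other way, and the SAP reports healing to 6 weeks while leaving the last PAR week open.

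It is also tempting to use Day 21 as the last post-debridement value against which to read Day 28. It is not a clean reference, because Visit 6 debridement is conditional too; and Day 21 PAR is already in the planned weekly table.

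**Conclusion.** The point holds in conditional form: as written, PAR can mix debridement states, and the SAP neither prevents nor reveals it. For a subject debrided at Visit 3 with no real change, Day 28 PAR is overstated by 9, 17 or 23 points at an assumed enlargement of 10%, 20% or 30%, and by less as true healing increases. The group mean bias is that amount multiplied by an unknown share, and is zero if nobody is debrided at Visit 3. The Day 42 bias runs in the opposite direction and arises only if imaging follows debridement.

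The consequence is limited. PAR is secondary and descriptive, the primary safety endpoint is untouched, and the debridement rules are the same in all arms. A reader might infer that the active-placebo comparison is biased towards Nu-3; the documents give no ground for that, since it would need debridement, or the tissue available to debride, to differ by arm. Nor do they say that absolute PAR will be used to plan the next study. The correction is worth making because it is cheap and because absolute PAR would otherwise carry an unlabelled shift.

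**What to change.** 1. **Protocol Synopsis, Section 4 and Schedule of Events.** Reconcile the post-debridement label on the 28-day imaging endpoint, and on the imaging row, with the no-debridement rule at Visit 7.
2. **Visit 8 text and Schedule of Events.** State that imaging is taken before any debridement, so that Day 42 matches Day 28. Footnote 1 of the schedule bars sharp debridement after Visit 2 while the table marks it as permitted at Visit 8; these entries also need to be reconciled. The point asks for no change in the debridement rules.
3. **CRF.** Record with each area whether debridement preceded the image, and of what type.
4. **SAP.** Add a sensitivity summary of Day 28 PAR, and of Day 42 PAR if reported, split by Visit 3 debridement status. The subset not debrided at Visit 3 is like-for-like. Visit 3 debridement is listed ahead of randomization, so if that order is followed the split is not affected by treatment. Flag any LOCF value carried across debridement states.

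The cost is wording, one or two CRF fields and one extra table, with no additional image or procedure. The limitation is precision: splitting arms of 12, 12 and 8 leaves small subgroups, and ulcers that needed no debridement may differ from the rest, so the split shows how much the state matters and does not replace the main summary.

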# 9. SCHEDULE OF EVENTS

	Scree	Screening		Treatment		EOS	Early Termination		
	Visit 1 Screening	Visit 2	Visit 3 Baseline	Visit 4	Visit 5	Visit 6	Visit 7 Final	Visit 8 Follow-up	ET
Event	-14 Day (±2 days)	-7 Day (±2 days)	Day 0 (±2 days)	Day 7 (±2 days)	Day 14 (±2 days)	Day 21 (±2 days)	Day 28 (±2 days)	Day 42 (±2 days)	
Eligibility Screening, Inclusion, Exclusion Criteria	Х		Х						
Informed Consent	Х								
Demographics & Medical History	Х								
Physical Exam	Х							Х	Х
Vital Signs	Х	Х	Х	Х	Х	Х	Х	Х	Х
Transcutaneous oxygen pressures, ABI's, doppler ultrasound and Ischemic Index	Х								
12 Lead ECG			Х				Х	Х	Х
Urine Pregnancy Test (2WOCBP)			Х						
Serum Pregnancy Test (  WOCBP)	Х		х		Х		х	Х	Х
Laboratory Tests – Safety Labs	X 		Х		Х		Х	Х	Х
Concomitant Medication and Adverse Event Review	X								
Visual Examination of Chronic Ulcer	Х	Х	Х	Х	Х	Х	х	Х	Х
Wound Culture Swab Pre- Debridement	Х		Х	X 6	X 	X 	X 6		X 
Microflora Swab Pre - Debridement	Х		Х	X 	X 	X 	X 		X 
Advanced digital imaging system Post -Debridement	х	х	Х	х	Х	Х	X 	Х	X 
Digital images before and after debridement (sponsor provided camera)	х	х	Х	х	х	х	X 	х	X 
Offloading	х	х	х	х	х	х	х	Study Off- Loading Ends	Study Off- Loading Ends
Subject Instruction Sheet Reviewed & Distributed	Х		х						
Randomization within RTSM			Х						
Dispense Test Article			Х	х	Х	Х			
Assess Subject Compliance Test Article Accountability				х	х	Х	Х		X 

ı	Debridement 1	SD-R	SD-P	LSD	LSD	LSD	LSD	None	SD-P	None
ı									il '	1 '

Sharp excisional debridement is required at V1 (SD-R), permissible (SD-P) at V2 and prohibited at subsequent visits. Only light debridement (LSD) is allowed at subsequent visits at the Investigator's discretion per appendix.

Women of childbearing potential (WOCBP) include any female who has experienced menarche and who has not undergone successful surgical sterilization (hysterectomy, bilateral tubal ligation, or bilateral oophorectomy) or is not postmenopausal [defined as amenorrhea >12 consecutive months]. Even women who are using oral, implanted, or injectable contraceptive hormones, an intrauterine device (IUD), barrier methods (diaphragm, condoms, spermicidal) to prevent pregnancy, practicing abstinence, or where partner is sterile (e.g., vasectomy performed at least six months prior to the subject's initiation of treatment) should be considered to be of childbearing potential.

At Visit 7 no debridement occurs but all imaging will still be captured

Only performed if early termination occurs prior to Visit 7

HbA1c collected

Swabs will not be performed if the wound is closed

## 10. DISCONTINUATION/WITHDRAWAL CRITERIA

# 10.1. Discontinuation of Study Treatment

Participation in this study and receiving the study treatment is voluntary. A subject can withdraw from the study treatment at any time. The Principal Investigator/treating physician based on his/her clinical judgement and evaluation may at his/her discretion discontinue study treatment for safety, behavioral, compliance, or administrative reasons.

If the subject withdraws consent for study treatment after beginning, study visits and all study procedures should still be completed. The sponsor may retain and continue to use any data collected during the study for a subject who has a withdrawal of consent for study treatment.

# 10.2. Withdrawal from the Study

A subject may withdraw from the study at any time at his/her own request or may be withdrawn at any time at the discretion of the investigator for safety, behavioral, compliance, or administrative reasons.

If the subject withdraws consent for disclosure of future information, the sponsor may retain and continue to use any data collected before such a withdrawal of consent.

If a subject withdraws from the study, he/she may request destruction of any samples taken and not tested, and the investigator must document this in the site study records.

See Schedule of Events for data to be collected at the time of study discontinuation and follow-up and for any further evaluations that need to be completed

